3.4 Investigational Site Selection

Investigational site selected to participate in this clinical study will be dependent on the Investigator at the site having the necessary resources to fulfill the clinical research requirements outlined in the protocol. These resources include adequate patient population, facilities and support staff to perform the clinical evaluation according to all applicable requirements.

3.5 Study Population

Candidates for this trial are patients being evaluated for placement of an arteriovenous fistula for chronic hemodialysis. Only patients meeting the inclusion and none of the exclusion criteria who signed Informed Consent Form (ICF) will be enrolled in the study.

3.5.1 Inclusion Criteria

1. Eligible for a native arteriovenous fistula.
2. Adult (age >18 years old).
3. Established, non-reversible kidney failure requiring hemodialysis (including pre-dialysis patients).
4. Target vein diameter(s) ≥ 2.0 mm or large enough to accommodate device diameter.
5. Target artery diameter ≥ 2.0 mm or large enough to accommodate device diameter.
6. Estimated life expectancy > 1 year.
7. Patient is free of clinically significant conditions or illness within 30 days prior to the AV fistula that may compromise the procedure

3.5.2 Exclusion Criteria

1. Known central venous stenosis or central vein narrowing $> 50\%$ based on imaging on the same side as the planned AVF creation.
2. Upper extremity venous occlusion(s) and/or vessel abnormality(ies) on the same side as the planned AVF creation that precludes endovascular AVF creation by everlinQ System as deemed by the interventionalists' clinical judgment.
3. Prior surgically created access in the planned treatment location.
4. Functioning surgical access in the planned treatment arm.
5. Pregnant women.
6. New York Heart Association (NYHA) class III or IV heart failure.
7. Hypercoagulable state.
8. Known bleeding diathesis.
9. Immunosuppression, defined as use of immunosuppressive medications used to treat an active condition.
10. Documented history of drug abuse including intravenous drugs within six months of AVF creation.
11. "Planned" concomitant major surgical procedure within 6 months of enrollment or previous major surgery within 30 days of enrollment.
12. Currently being treated with another investigational device or drug.
13. Known allergy to contrast dye which cannot be adequately pre-medicated.

14. Known adverse effects to sedation and/or anesthesia which cannot be adequately pre-medicated.
15. Patients who do not have an ulnar or radial artery.
16. At the time of procedure distance between target artery and vein will not allow magnets to align vessels sufficiently to create the fistula.
17. Evidence of active infections on the day of the index procedure.
18. Written informed consent not obtained.

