1.1 Device Description

The TVA Medical everlinQ System that will be used in this study is an investigational device, and is not cleared by FDA or any competent authority for sale in the US or elsewhere.

The everlinQ device is a single-use disposable device. The everlinQ catheter system consists of two flexible, magnetic catheters. One (venous) catheter contains an electrode to deliver radiofrequency (RF) energy, and has a cord that is connected for a remote hand switch. The venous catheter and hand switch, along with a standard grounding pad, connect to a standard electrosurgical unit for the delivery of RF energy. The second (arterial) catheter is a flexible magnetic catheter that contains a backstop for the RF electrode of the venous catheter to interface. Once the catheters are properly inserted and aligned, the magnets contained in each catheter attract to one another, approximating the vessels while simultaneously aligning the electrode with the backstop. RF energy is delivered to the electrode whereby the arterio-venous fistula (AVF) is created.

For additional details regarding device or its principal of operation, please refer to the most current Instruction for Use (IFU).

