2.2 Risks

Many of the potential risks and complications associated with the everlinQ System and procedure are similar to the risks expected for CKD patients undergoing surgically created arteriovenous fistula (AVF) procedures. The potential risks related to the everlinQ System and procedure are similar to surgical AVF creation and may include but not limited to:

- Bruising
- Numbness, tingling and/or coolness in the fistula extremity
- Occlusion/stenosis (AVF clots)
- Thrombosis (AVF completely clotted and cannot be used)
- Failure to mature (AVF can never be used)
- Additional procedures (interventions)
- Venous hypertension (arm swelling)
- Aborted or longer procedure
- Swelling, irritation or pain
- Bleeding, hematoma (a solid swelling of clotted blood within the tissues) or hemorrhage (an escape of blood from a ruptured blood vessel)
- Wound problem
- Fever (pyrogenic reaction)
- Steal or ischemia (not enough blood flow to hand)
- Embolism (blood clot or device piece)
- Infection (local or in the blood (bacteremia))
- Increased risk of congestive heart failure (heart fails due to increased flow from AVF)
- Vessel, nerve or AVF damage or rupture
- Pseudoaneurysm (leaking hole in artery that forms blood clot on outside of it)
- Heart problems such as arrhythmias (abnormal beats) that can be caused due to high levels of potassium in the blood (mostly due to CKD and not the TVA device or procedure)
- Death (mostly due to CKD related complications not the TVA device or procedure)
- Burns
- Problem due to sedation or anesthesia
- Sepsis (systemic inflammatory reaction)
- Toxic or allergic reaction
- Electrocution

In addition, fistula infiltration injury due to needle cannulation of the fistula is also a known risk/event.

Most of these potential risks also exist for creation of standard (surgical) AVFs. There may also be other risks related to use of the everlinQ System and procedure that are not listed or that are not known at this time. This study will help characterize the adverse events associated with the everlinQ System.

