3 STUDY METHODOLOGY

3.1 Study Design

This is a prospective, single-center study to evaluate the everlinQ System when used to create an endoAVF in hemodialysis patients. A total of up to 50 subjects will be enrolled and will undergo an endoAVF creation procedure using the everlinQ System. All subjects will be followed for up to 12 months post index procedure based on Investigator's discretion.

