4.2 Screening Evaluation

All patients considered for enrollment must undergo a thorough screening evaluation prior to the scheduled treatment with the everlinQ System. The screening evaluation includes:

- Collection of demographic data;
- A medical history and physical exam;

- A laboratory evaluation (i.e. blood tests); and
- A duplex ultrasound and optional angiography/venography assessment.

There will be a final assessment of the suitability of the patient's study eligibility due to vascular anatomy or other criteria made at the time of the index procedure and thus, there may be some consented subjects who are determined to be ineligible who will not be enrolled in the study.

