6.6 Protocol Deviations

A Protocol Deviation CRF must be completed for each deviation from the Study Protocol that occurred at the site (e.g., failure to obtain informed consent, enrolling a patient who does not meet inclusion/exclusion criteria, not performing required testing, missed follow-up visits, etc.).

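### A magnet-alignment failure found after catheter insertion can be classed as a procedure-day exclusion and so drop out of technical success

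*Combined protocol and SAP*

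**What the plan says.** Item 16 of section 3.5.2 reads: "At the time of procedure distance between target artery and vein will not allow magnets to align vessels sufficiently to create the fistula". It gives no distance threshold, no method of measurement, and no statement that the judgement is complete before the device is inserted.

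Section 1.1 places the magnets inside the two catheters: "Once the catheters are properly inserted and aligned, the magnets contained in each catheter attract to one another".

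Section 3.5 makes enrolment depend on eligibility: "Only patients meeting the inclusion and none of the exclusion criteria who signed Informed Consent Form (ICF) will be enrolled in the study". Section 4.2 provides for a final assessment "due to vascular anatomy or other criteria made at the time of the index procedure" and adds that "there may be some consented subjects who are determined to be ineligible who will not be enrolled in the study". No section names the event that marks enrolment.

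Section 3.1 sets a cap of 50 subjects, who "will be enrolled and will undergo an endoAVF creation procedure using the everlinQ System". Section 3.3 defines technical success as a fistula that was created and is still patent 1 to 7 days later, without a denominator. Central venous catheter use is the only endpoint there that is expressed per enrolled subject. Section 5 defines no analysis population. Section 6.9 requires case report forms for enrolled patients and is silent on subjects who were attempted but not enrolled. Section 3.3 also states that there are no formal hypothesis tests.

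**The concern.** Bringing the vessels together with the magnets is a step in using the device. If item 16 may be invoked after the catheters are in, the same event is both a device failure and a ground for non-enrolment, and the choice is made with the result already known. That is an outcome-dependent exclusion, not just a missing detail.

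The bias has one direction. Each omitted attempt is a failure taken out of the denominator, so the reported rate can only rise. Other failures, such as failed energy delivery or a fistula that is not patent at 1 to 7 days, would still count.

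The study is single-arm and descriptive, so the reported percentages are its result. A reader could not tell whether the technical success rate is per attempt or per subject retained after a procedure-day exclusion.

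**Working it through.** **Step 1: follow one subject through the text.** A consented subject passes screening. Both catheters are inserted. The vessels lie too far apart and the magnets do not align them.

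- Item 16 is met as worded: it is the time of the procedure, and distance prevents alignment.
- Section 4.2 then applies: a subject found ineligible at the index procedure is not enrolled.
- If technical success is taken over enrolled subjects, this subject does not appear in it.
- If it is taken over attempts, this subject is a failure.

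No sentence in sections 3.3, 3.5, 4.2 or 5 chooses between the last two.

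**Step 2: size.** The plan gives no expected success rate and no expected number of such cases, so there is no figure of its own to reproduce. Only the cap of 50 comes from the documents (section 3.1). The success counts and the number of omitted attempts, *k*, are assumptions.

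*Reading A: the cap counts retained subjects, and the k attempts lie outside it.* Reported rate = s/50; rate per attempt = s/(50 + k). With s = 48, the reported rate is 48/50 = 96.0% (exact Clopper-Pearson 95% CI 86.3 to 99.5) whatever *k* is.

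| k | Per attempt | Exact 95% CI | Overstatement (points) |
|---|---|---|---|
| 0 | 48/50 = 96.0% | 86.3 to 99.5 | 0 |
| 1 | 48/51 = 94.1% | 83.8 to 98.8 | 1.9 |
| 2 | 48/52 = 92.3% | 81.5 to 97.9 | 3.7 |
| 5 | 48/55 = 87.3% | 75.5 to 94.7 | 8.7 |

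*Reading B: the cap counts all attempts, and k of the 50 are dropped.* Assume two other failures, so s = 48 − k. Reported rate = s/(50 − k); rate per attempt = s/50.

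| k | Reported | Per attempt | Overstatement (points) |
|---|---|---|---|
| 1 | 47/49 = 95.9% | 47/50 = 94.0% | 1.9 |
| 2 | 46/48 = 95.8% | 46/50 = 92.0% | 3.8 |
| 5 | 43/45 = 95.6% | 43/50 = 86.0% | 9.6 |

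The two readings agree: about 2 points for one omitted attempt and about 4 for two. The k = 5 row is an upper illustration, not an expectation. In both tables the reported rate hardly moves with *k*, so it carries almost no information on alignment failures.

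**The case against.** The strongest reply is that item 16 is a check made before insertion. Its wording is anatomical and predictive, and the next item is a check on the day of the procedure. The non-enrolment sentence stands under the screening heading and refers to vascular anatomy. Table 1 marks angiography or venography at the index procedure without the optional footnote. On that reading the effect is zero. It may well be the intended reading, but the text does not say so, and one clause would settle it.

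It can also be said that the size rests on assumed counts, that one or two cases move the rate by less than the width of its own confidence interval, and that nothing is tested. All of this stands and keeps the point small. It does not remove it, because the shift is systematic and not random.

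Two stronger readings are tempting, and the documents support neither.

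- A reader might infer that other sections contradict section 4.2: section 3.1 has subjects enrolled and then treated, section 6.6 lists "enrolling a patient who does not meet inclusion/exclusion criteria" as a deviation, and section 2.2 lists "Aborted or longer procedure" as a risk. All three fit one sequence: consent, procedure-day check, enrolment, procedure. The gap is that nothing says where the check ends.
- A reader might infer that the safety window is undefined when no fistula was made, or that adverse events in such subjects would be lost. Section 4.5.1 equates the index procedure with fistula creation and covers attempted treatment. Section 4.5 counts events from the start of treatment and includes those from device operation or malfunction. Table 1 collects events from the index procedure. The device log (section 6.8) records patient IDs for used devices, and the sponsor requests procedural reports (section 6.10). Loss of these data is therefore less likely, although section 6.9 does not expressly require forms for such subjects.

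**Conclusion.** The point holds as a minor one. Applied literally, the plan allows a post-insertion alignment failure to be classed as non-enrolment and left out of technical success. The effect can only favour the device. Its size is unknown: zero if item 16 is used only before insertion, and about 2 or 4 percentage points for one or two omitted attempts, given roughly 50 subjects and an assumed reported rate near 96%. No error rate, test or decision rule depends on it. What is affected is how the published percentage can be read.

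**What to change.** For counting purposes:

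1. Define enrolment as the first attempted insertion of an everlinQ catheter.
2. Use all such subjects as the denominator for technical success and for the safety percentage.
3. Let item 16 remove a subject from the analysis only if it was met before insertion, and count later non-alignment as a technical failure.
4. Require case report forms for every attempted subject.
5. Report the number of procedure-day exclusions, split into before and after insertion.

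The cost is short wording changes in sections 3.1, 3.3, 3.5.2, 4.2 and 6.9, possibly a slightly less favourable technical success rate, and a few extra case report forms with 3-month adverse event follow-up. The change concerns counting only. It does not touch the decision to proceed with or stop a procedure.

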4 STUDY SCREENING AND FOLLOW-UP PROCEDURES

Patients are required to undergo a thorough screening evaluation prior to the index procedure and return for evaluations according to the study follow-up schedule indicated in Table 1. Study data will be collected on case report forms (CRFs) provided by the Sponsor. Any site's standard of care tests may be done outside of the study (e.g., prior to study participation).

Table 1: Schedule of Study Procedures

Assessment	Screening	Index Procedure	Post Index Procedure				
			1-7 Days	30-45 Days	3 Months	6 Months (Optional) ¹	12 Month (Optional) ¹
Compliance window	-30 days	Day 0	1-7 days	30-45 days	Anniversary date + 14 / -7 days	Anniversary date + 45 / -15 days	Anniversary date + 60 / -30 days
Informed Consent	X						
History, Physical Exam, Laboratory Evaluation	X						
Ultrasound Evaluation	X	X ¹	X	X	X	X ¹	X ¹
Angiography/Venography	X ¹	X	X ¹	X ¹	X	X ¹	X ¹
Adverse Events		X	X	X	X	X	X
Dialysis Access Data				X ²	X ²	X ²	X ²

¹ Optional visit at the discretion of the Primary Investigator
² Will be obtained after dialysis is initiated using endoAVF created by the everlinQ System.

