An AVF is traditionally created during a surgical procedure under general anesthesia. A surgical incision is made in the forearm or upper arm, followed by identification of target arteries and veins for surgical connection. Frequently, prior to the procedure, the vessels are mapped using duplex ultrasound imaging, allowing for pre-operative vessel diameter measurement and vessel selection. Typically, the radial artery or brachial artery and the cephalic vein or basilic veins are selected. The target vessels are carefully dissected and mobilized, and the vein is transected. An arteriotomy is created, and an anastomosis is sewn between the vein and the artery. After completion, the flow is verified using palpation and ultrasound, and the incision is closed. Over the course of the following 1 - 3 months, the AVF gradually matures, that is, the vein dilates and accepts increased flow sufficient for hemodialysis.

Though there is widespread agreement that the AVF is the preferred method of vascular access, 28 – 60% of AVFs do not successfully mature and are rendered unusable for hemodialysis.^{10,12} This has unintended consequences for patients in immediate need of hemodialysis, since a tunneled dialysis catheter must often be placed. Catheters are associated with higher morbidity, mortality, and costs and are therefore considered a last resort.¹¹

To improve on these results, and decrease the invasiveness of the procedure, a new tool and method for creation of an AVF has been developed, called everlinQ system. The system uses two devices,

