3.3 Study Endpoints

Study endpoints will be summarized using descriptive statistics. There are no formal hypothesis tests associated with these endpoints.

- **Technical success:** Verification that an endoAVF has been created and remains patent 1-7 Days after the index procedure. Patency will be determined by experienced examiner as the presence of a bruit that is detected with stethoscope, or presence of thrill, or via Duplex Ultrasound, or via angiogram.
- **Fistula Maturation:** defined as endoAVF that is free of stenosis or thrombosis, with brachial artery flow of at least 500 ml/min and at least 4 mm vein diameter (as measured by duplex ultrasound) OR patient was dialyzed using 2 needles.
- **The Time to Fistula Maturation:** the number of days between the date of AVF creation and the date of endoAVF maturation (based on primary efficacy endpoint definition of maturation).
- **Duration of Central Venous Catheter Exposure:** The rate of CVC use per enrolled subjects at 30-45 Days and other follow-up visits. The analysis will be performed for pre-dialysis and on dialysis patients, as applicable.
- **EndoAVF-related Re-intervention Rate:** The re-intervention rate for endoAVF (defined as any intervention required to maintain or re-establish patency) will be calculated at each available follow-up visit post index procedure.
- **Primary Patency:** The primary patency rate will be determined via Kaplan-Meier methods and based on the time of endoAVF creation until any intervention designed to maintain or reestablish patency or endoAVF abandonment.
- **Secondary Patency:** The secondary patency rate will be determined via Kaplan-Meier methods and based on the time of endoAVF creation until access abandonment. Abandonment due to renal transplant receipt will not be included in this endpoint assessment.
- **Safety:** The safety endpoint is the percentage of patients who experience one or more serious device -related adverse events during the first 3 months following AVF creation.

Additional exploratory analysis:

- Rate of serious procedure-related events will be reported at 3 months.
- Rate of serious device-related event rate will be reported at 3 months.
- Rate of device and/or procedure-related infections at 3 months.
- Arterial and arterialized vein flow rates and diameters will be measured via DUS at 30-45 Days and at each available follow-up visit post index procedure.

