4.4.2 Patient Disposition

The Patient Disposition Case Report Form should be completed whenever a patient exits the study. This includes patients enrolled in the study who:

- complete the study protocol,
- withdraw from the study,
- are lost to follow-up,
- are deceased,
- have other reason(s) for exiting the study.

4.5

Adverse Events

For the purpose of this protocol, an AE will be defined as any adverse medical change (i.e., *de novo* or increased severity in a preexisting condition) from the subject's baseline condition that occurs during the course of the clinical study, after starting treatment, whether considered treatment-related or not. "Treatment" includes all investigative or commercially-approved products administered according to the Study Protocol.

Any pre-planned procedures, interventions, etc. or expected progression of pre-existing conditions (e.g., cancer progression) will not be considered AEs for this study. In addition, normally expected symptoms caused by the treatment are not considered an AE for this study. These may include but are not limited to:

- Transient arterial spasm resolving spontaneously OR with medication only.
- Minor discomfort or bruise at the arterial access place.
- Small amount of bleeding at point of arterial access.
- Transient numbness, tingling or coolness that resolved within 4 weeks post index procedure.
- Bruising at the AVF creation site.
- Side effects of standard-of-care medications.
- Hematoma at the arterial and/or venous access site(s) managed prior to patient discharge and did not adversely affect patient discharge.

Only AEs that are relevant to index procedure, study device, access site or AVF will be collected in the study. For example, if the patient has knee replacement or undergo hysterectomy, these events will be considered as non-study related and will not be required to be recorded via Adverse Event form.

AE Type	Definition

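### Table 1 defers dialysis access data until the endoAVF is in use, so the catheter-use endpoint has no scheduled data for subjects not yet dialysed through it

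*Combined protocol and SAP*

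**What the plan says.** Section 3.3 lists an endpoint titled Duration of Central Venous Catheter Exposure and defines it as "The rate of CVC use per enrolled subjects at 30-45 Days and other follow-up visits". It adds: "The analysis will be performed for pre-dialysis and on dialysis patients, as applicable". Inclusion criterion 3 (section 3.5.1) admits pre-dialysis patients, so both groups will be enrolled.

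Table 1 in section 4 has one row on dialysis access, Dialysis Access Data. It is blank at screening, at the index procedure and at 1-7 days. It is marked at 30-45 days and at 3, 6 and 12 months, and each of those marks carries footnote 2: "Will be obtained after dialysis is initiated using endoAVF created by the everlinQ System". The protocol does not define the row's content, and the case report forms (CRFs) are not part of the document.

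The Introduction says that "28 – 60% of AVFs do not successfully mature and are rendered unusable for hemodialysis", and that this affects patients in immediate need of dialysis, "since a tunneled dialysis catheter must often be placed". On timing it says: "Over the course of the following 1 - 3 months, the AVF gradually matures".

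**The concern.** The endpoint needs catheter status for every enrolled subject at every visit from 30-45 days. The schedule makes access data conditional on the endoAVF being in use. Whether a subject is observed therefore depends on something closely tied to the outcome, because the protocol itself names a catheter as the usual consequence of a fistula that cannot be used.

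Two groups fall outside the condition: subjects dialysed by catheter while the endoAVF is not usable, and pre-dialysis subjects who start dialysis on a catheter. Subjects who already use the endoAVF and still have a catheter in place are past the condition and are covered.

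Section 5 gives no rule for missing status. If unobserved subjects are counted as catheter-free, the per-enrolled rate is understated. If they are left out, the rate describes only subjects already using the endoAVF, which is not the stated denominator. That error can go either way, because pre-dialysis subjects without a catheter are unobserved too.

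A related problem is that the title promises a duration while the definition is a per-visit rate, and the protocol specifies no catheter insertion or removal dates.

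**Working it through.** The plan states no figure for this endpoint, so there is none to reproduce. The check compares the passages and then illustrates the possible size.

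**Is catheter status scheduled anywhere else?**

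- History, physical exam and laboratory evaluation are marked at screening only (Table 1, section 4.2).
- Ultrasound is specified for flow rates and diameters of the target vessels (sections 3.3 and 4.2.1).
- Adverse event reporting is restricted: "Only AEs that are relevant to index procedure, study device, access site or AVF will be collected in the study" (section 4.5). An adverse event there is a change from baseline, so a catheter already present at baseline is not one. A report of failed maturation might mention a new catheter, but would not give status at each visit.
- Section 4.4.1 names a Follow-Up Visit CRF without describing its fields.

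**Two readings of the row.** If Dialysis Access Data includes access type, footnote 2 excludes the two groups above. If it covers only endoAVF cannulation, CVC status is scheduled for nobody. Neither reading supplies the endpoint.

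**Number without scheduled data.** Inputs: N = 50, the maximum enrolment (section 3.1); u = share of endoAVFs not usable, taken as 0.28 to 0.60 from the Introduction. That range concerns existing AVFs, so applying it here is an assumption.

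N × u = 50 × 0.28 = 14, and 50 × 0.60 = 30.

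These counts leave out pre-dialysis subjects with a mature endoAVF who never start dialysis. Given 1-3 months to mature, the share not yet usable at 30-45 days is probably higher.

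**Bounds without a catheter-use assumption.** With x observed CVC users and m unobserved subjects, the per-enrolled rate lies between x/N and (x + m)/N. If no observed subject has a CVC (x = 0), that is 0% to 14/50 = 28%, or 0% to 30/50 = 60%.

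**Understatement if unobserved counts as catheter-free.** Further assumptions: D of the 50 are on dialysis; every dialysis subject without a usable endoAVF uses a catheter; no pre-dialysis subject starts on one; a share r of cannulated subjects still has a CVC.

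- True rate = [D·u + D·(1 − u)·r]/N
- Recorded rate = D·(1 − u)·r/N
- Gap = D·u/N, whatever r is

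| D | Gap, u = 0.28 | Gap, u = 0.60 |
|---|---|---|
| 20 | 5.6/50 = 11.2 points | 12/50 = 24.0 points |
| 30 | 8.4/50 = 16.8 points | 18/50 = 36.0 points |
| 40 | 11.2/50 = 22.4 points | 24/50 = 48.0 points |

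Paired rates for D = 30 and r = 0.5:

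- u = 0.28: true (8.4 + 10.8)/50 = 38.4%, recorded 10.8/50 = 21.6%.
- u = 0.60: true (18 + 6)/50 = 48.0%, recorded 6/50 = 12.0%.
- u = 0.70 (assumed, for an early visit): true (21 + 4.5)/50 = 51%, recorded 4.5/50 = 9%.

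If only 80% of the uncannulated dialysis subjects use a catheter, the D = 30 gap becomes 0.8 × 16.8 = 13.4 to 0.8 × 36.0 = 28.8 points.

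**Error if unobserved subjects are dropped.** The reported rate is then r. With r = 0.5:

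- D = 20, u = 0.28: true (5.6 + 7.2)/50 = 25.6%, an error of +24.4 points.
- D = 40, u = 0.60: true (24 + 8)/50 = 64.0%, an error of −14.0 points.

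**The case against.** The strongest defence is that Table 1 schedules procedures and is not a list of data fields. Data are collected on sponsor CRFs, and a Follow-Up Visit CRF exists that may already record catheter status. Other endpoint data, such as re-intervention and abandonment, have no row of their own either. If the row means cannulation details only, footnote 2 is sensible and there is no direct contradiction. In addition, a catheter newly placed after failed maturation might be picked up as an AVF-related adverse event.

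Part of this stands. The documents do not show that the data will be lost, only that the protocol does not provide for collecting them. But a missing row is a different matter from a row with an explicit condition that excludes the relevant subjects: a site following footnote 2 literally would record nothing for them and commit no deviation. The cannulation-only reading makes the gap wider, and adverse event reports cannot give prevalence by visit.

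The figures are also open to challenge. D, r and u = 0.70 have no source in the documents, 50 is an upper limit, and the Introduction says a catheter is often needed, not always. They show the possible size and do not forecast it. The 0-28% and 0-60% bounds need the fewest assumptions.

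**Conclusion.** The concern holds. The protocol defines a CVC rate over all enrolled subjects but does not schedule catheter status for those not yet dialysed through the endoAVF, who include those most likely to depend on a catheter. That conclusion rests on the text alone.

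The size is illustrative. Across the cases tabulated, counting unobserved subjects as catheter-free understates the rate by 11 to 48 percentage points; leaving them out changes the denominator, and the direction of error is then unsettled.

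The point should be fixed, but its reach is limited: one descriptive endpoint in a single-center pilot, with no effect on any hypothesis test, the sample size or the safety endpoint.

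**What to change.** - Restrict footnote 2 to details of endoAVF cannulation.
- Record dialysis status and current access (CVC, endoAVF, other, none) for every enrolled subject at screening and at each follow-up visit from 30-45 days, whether or not the endoAVF is in use, with CVC insertion and removal dates.
- Report CVC prevalence at each visit over enrolled subjects, by baseline dialysis status. Show missing status separately and do not count it as no CVC.
- If the title keeps Duration, also report catheter-days per subject. Otherwise retitle the endpoint as a rate.

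The cost is a table footnote and a few CRF fields, some of which may already exist. No visit or procedure is added. Reported CVC use may look less favourable than under the present schedule. The change is best made before follow-up data accrue, since unrecorded status may be hard to recover later.
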